4 STUDY DESIGN

4.1 OVERALL DESIGN

This study is an open-label, randomized, multi-site trial to evaluate the effectiveness of an oral health intervention among individuals with mild dementia.

There will be two sites for the intervention: Duke University in Durham, North Carolina, U.S., and New York University, NY. At these sites, recruited dyads will be randomly assigned to one of three groups; Treatment group 1, Treatment group 2, and Control group. IRB approval will be obtained from these two participating sites.

The study lasts 6 months. The first three months is the active intervention phase in which coaching and educational modules are delivered to Treatment group 2. The second three months is the maintenance period in which no coaching or educational modules are presented to participants or care partners. As a team, the study coordinator, the dental hygienist, and the interventionist will conduct three visits with the participants and their care partners; baseline, 3-month (end of the active intervention phase), and 6-month (end of three-month maintenance phase).

Prior to the first study visit, Study Coordinators will pre-screen potential participants based on the inclusion and exclusion criteria. They will obtain basic medical history and verbal informed consent. If participants qualify for the study, the coordinator will schedule the first study visit with the participant and their care partner within the six weeks. Because the procedures and personnel involved in the study visits differ based on the arm of the study to which a participant is assigned, randomization must be done prior to the first visit.

The study participants will be instructed not to eat or brush their teeth for one hour before the scheduled visit and oral health evaluation. During the visit, the dental hygienist will conduct an oral health evaluation. A standard booklet of oral health educational materials will be given to all participants. Additional intervention elements apply to the treatment groups:

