5.2 EXCLUSION CRITERIA

Any participant who meets any of the following criteria will not qualify for entry into the study:

- The participant is unable to have an oral health evaluation.
- The participant is prescribed anti-biotics prior to a regular dental visit.
- In the opinion of the investigator, the participant has sensory or physical problems that prevent participation in the intervention.
- In the opinion of the investigator, the participant has a terminal illness or behavioral or psychiatric disorder that would interfere with participation in the intervention.
- The participant has a medical condition that places him/her at greater risk of infection from the manipulation of the gums to measure the gingival index. These conditions are serious congenital heart conditions, previous infective endocarditis, prosthetic cardiac valves, and cardiac transplantation with cardiac valvulopathy.
- The participant has a medical condition that suppresses the immune system.
- The participant has had a total joint replacement and has had an infection in the replaced joint.
- The participant is at increased risk of bleeding due to a bleeding disorder such as having hemophilia or the use of antiplatelet or anticoagulant medications.

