6.3 MEASURES TO MINIMIZE BIAS: RANDOMIZATION AND BLINDING

The study team plans to take numerous steps to ensure a rigorous, unbiased study. Prior to the first visit, the statistician will be blinded when randomizing participant and care partner to study groups.

The procedures for the study visits differ based on which arm of the study a participant is assigned; thus, the research staff is not blind to the participant's assigned group. The randomization group determines which research staff members attend the home visits. The Research staff who conduct the study visits with participants and care partners will be trained to adhere to study procedures and interventions appropriately based on group assignment. The interventionist does not attend the visits for the Control Group and Treatment Group 1, reducing risk of contamination through delivery of in-person coaching. The participants will be recruited from local clinics and the intervention will be conducted at each participant's home, so the chances of contamination between the Treatment groups and the Control group is small.

Blinded randomization assignments will be determined by the statistician at the beginning of the study using a block (by sex) random allocation algorithm generated *a priori* by the statistician assuring there will be equal allocation to arms by site. Because the interventionist does not attend study visits for participants in the Control Group and Treatment Group 1, randomization must be done prior to the first visit.

This is a three-group randomized trial [Treatment Group 1, Treatment Group 2 and the Control Group] using randomization blocks by site to ensure balance within this potential confounder. Each randomization block will be composed of two units male and female in each treatment arm by site and randomization error will be minimized by ensuring that an equal number of all of units are randomized to each group. As minorities are recruited, they will sequentially be assigned to each group. To assess for randomization balance, we will use chi-square tests to examine if there are any statistically significant differences between race, and site by the three groups.

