8 STUDY ASSESSMENTS AND PROCEDURES

8.1 ENDPOINT AND OTHER NON-SAFETY ASSESSMENTS

Screening

Telephone screening will be conducted to determine eligibility. The study coordinator will first confirm that both the participant and the care partner are interested in participating in the study. After obtaining permission from the participant to ask the care partner questions about the participant's health and every day activities, the care partner will then be asked questions about the functional abilities and health conditions of the potential participant to determine eligibility (See Oral Health Study Phone Screening Report Form). Preliminary eligibility will be determined by the study coordinator at the end of the call. The PI or designee at each site will then review the responses to the health conditions and determine final eligibility. The screening interview should occur within 42 days of enrollment.

Home Visits

The care partner and participant will complete the questionnaires in separate rooms from one another.

Participant Questionnaire:

- Sociodemographics (Baseline) for the study participant including date of birth, gender, years of education completed, race/ethnicity, marital status
- Oral Health Knowledge Scale: Our team has developed a 12-item oral health knowledge scale to assess the knowledge of oral self-care such as frequency and technique of brushing and flossing, duration of brushing, and tongue cleaning that are consistent with general recommendation by dental professionals.³⁷ Oral hygiene behavior (investigator developed) asks about participants' frequency of toothbrushing, flossing, and mouth rinse. The response categories will be coded as 1= Twice a day or more, 2=once a day, 3= Several times a week, 4= Once or less than once a week, 5=Hardly ever, and 6= Never. Geriatric Oral Health Assessment Index³⁸ asks 13 questions about self-perceived oral health. The response categories of each item range from 1=always, 2=sometimes, and 3=never. Xerostomia Inventory³⁹ asks 11 questions about the signs and severity of xerostomia⁸. The responses of each question range from 1=never, to 5=very often. PHQ-8⁴⁰ is an 8-item screen for depression that is administered to the participant.

Care Partner Questionnaire:

- Sociodemographics (Baseline) for the care partner including date of birth, gender, years of education completed, race/ethnicity, marital status, and medical and dental insurance for care partner and for the participant

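### Small fixed blocks printed in the protocol, sequential assignment of minorities and no described concealment let staff who judge eligibility predict part of the allocation

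*Combined protocol and SAP*

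**What the plan says.** **Sequence.** Section 6.3 of the protocol has the statistician make the list in advance: "Blinded randomization assignments will be determined by the statistician at the beginning of the study". Blocking is by sex and site, with one stated composition: "Each randomization block will be composed of two units male and female in each treatment arm by site". Balance is enforced by "ensuring that an equal number of all of units are randomized to each group". The same paragraph says that minorities, as they are recruited, are assigned sequentially to each group. The Study Design section of the SAP mentions stratification by site and does not mention sex.

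**Concealment.** Section 6.3 calls the assignments blinded. It describes no central release, no envelopes and no variation in block size.

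**Who knows past assignments.** Section 4.1 states: "This study is an open-label, randomized, multi-site trial". Section 6.3 adds that "the research staff is not blind to the participant's assigned group", and that the group decides which staff attend the home visits. Section 6.2.1 has coordinators and principal investigators debrief weekly. Section 4.1 also says "There will be two sites for the intervention", so each team has only its own short sequence to follow.

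**Who decides entry.** In section 8.1 the coordinator judges preliminary eligibility by telephone, and then "The PI or designee at each site will then review the responses to the health conditions and determine final eligibility". Two exclusions in section 5.2 are left to judgement, for example "In the opinion of the investigator, the participant has sensory or physical problems that prevent participation in the intervention". Randomization comes before the first visit (6.3). Written consent (10.1.1.2) and the medication review that confirms eligibility (8.1) take place at that visit.

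**The concern.** Having a statistician draw the list protects the sequence when it is generated. It does not hide the next arm from someone who knows the block composition and has seen the assignments so far. Here the composition is in the protocol, assignments are visible in an open-label trial, and the people who see or discuss them also decide who enters and when the first visit is booked. A dyad thought easier to coach could be booked when Treatment Group 2 (TG2) is likely to come next, or a difficult one when control is.

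There is a second route. Consent and the medication check follow randomization, so a dyad can decline or be declared ineligible once its arm is known. The accrual table that precedes the SAP's Study Design section leaves ineligible dyads out of its counts.

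At stake is the comparability of the arms on features that the analysis does not measure.

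**Working it through.** The documents give no figure for predictability, so there is none to reproduce.

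**Inputs.** Three arms, equal allocation, and two sites by two sexes, giving four strata (6.3, 4.1). Planned size 120 dyads (1.1); 60 consented as of 05/08/24, 20 per arm (accrual table). I assume complete blocks and a guesser who knows the block length, the stratum and all past assignments in it.

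**Readings of the block sentence.**
- One male and one female per arm: length 3 within a site-by-sex stratum.
- Two of each sex per arm: length 6 within a site-by-sex stratum.
- Two of each sex per arm, with site as the only stratum: length 12.

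**Predictability.** With places a, b, c left in the block, the best guess is right with probability max(a, b, c)/(a + b + c). The next arm is certain when only one arm has places left. Averaging over all orderings of a block:
- Length 3: correct (1/3 + 1/2 + 1)/3 = 0.611; certain 1/3.
- Length 6: correct 3.367/6 = 0.561; certain 1.2/6 = 0.200.
- Length 12: correct 6.144/12 = 0.512; certain 1.333/12 = 0.111.
- Simple randomization: correct 0.333; certain 0.

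| Block length | Certain | Best guess correct | Certain among 60 | Certain among 120 |
|---|---|---|---|---|
| 3 | 33% | 61% | 20 | 40 |
| 6 | 20% | 56% | 12 | 24 |
| 12 | 11% | 51% | about 7 | about 13 |

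If the sequential rule means strict rotation, the next arm for a minority dyad is certain once the order has been seen.

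**Illustrative bias.** The documents give no steering size, so I assume that dyads are 0.3 SD better when staff expect TG2 and 0.3 SD worse when they expect control. Let w be +1, −1 or 0 accordingly. The raw shift is 0.3 × (mean of w for TG2 dyads − mean of w for control dyads).
- *Wide rule*: staff act whenever more TG2 than control places remain, or fewer. At length 3, w for a TG2 dyad averages 0 in first position, 1/2 in second and 1 in third, so the mean is 1/2. For control it is −1/2 by symmetry. Shift = 0.3 × 1 = 0.30 SD.
- *Strict rule*: staff act only when TG2 or control is the single likeliest arm. At length 3 only third position counts, so the means are 1/3 and −1/3. Shift = 0.3 × 2/3 = 0.20 SD.
- The same enumeration gives 0.25 and 0.17 SD at length 6, and 0.20 and 0.14 SD at length 12.

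The shift is proportional to the assumed steering. With 0.1 SD in place of 0.3, every figure is divided by three, so the full range of 0.14 to 0.30 becomes about 0.05 to 0.10 SD.

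**Scale of the planned effect.** Section 9.2 gives an effect size of 0.3 and a minimum of 107 subjects. A 2-df chi-square test with noncentrality N × 0.3² reaches 80% power at the 0.05 level at N = 107.05, so 0.3 fits as Cohen's f. A two-group difference of 0.3 SD would need 175 per arm. With three equal arms, f = 0.3 means a largest gap between arms of 0.3/(√2/3) = 0.64 to 0.3/√(1/6) = 0.73 SD, depending on where the middle arm lies.

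**The case against.** The list is made by the statistician, assignments are described as blinded, and nothing says that site staff hold the list. For most dyads staff could only guess. This stands, and it limits the point to predictability from block structure and from the sequential rule.

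The planned analysis removes part of any bias. The SAP's Aim 1 model adjusts for baseline index scores and baseline functional status, and its test is the group-by-time interaction, on which a stable baseline difference does not load. Eligibility is settled by telephone before the oral evaluation, so staff cannot steer on observed plaque or gingival scores. This also stands. Selection on traits that predict response to coaching but are not in the model, such as motivation or care-partner engagement, would remain.

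A reader might infer three stronger conclusions that the documents do not support:
- *That selection took place.* The 20/20/20 split has probability 1.4% under simple randomization, but that is what forced balance produces. It says nothing about who was enrolled.
- *That staff know each next arm.* Certainty covers 11% to 33% of assignments, plus minority dyads if they are strictly rotated.
- *That the bias could equal the whole planned effect, because both can be written as 0.3.* The first is a raw SD shift under an assumed steering size, before adjustment. The second fits 107 subjects only as Cohen's f.

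Finally, accrual may be over: the SAP describes randomization in the past tense, and section 9.4.9 reports enrollment below plan. That would make a new list moot, but not the checks on dyads already randomized.

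**Conclusion.** The weakness holds on every reading of the block sentence. Between 11% and 33% of assignments can be known in advance and 51% to 61% guessed, against 33% by chance, provided that staff know the printed composition and the past assignments in their stratum. Literal rotation of minorities would be more predictable still.

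Selection bias is therefore possible, but its presence and size are unknown. Under an assumed steering of 0.3 SD, the raw TG2-control shift is about 0.17 to 0.30 SD for blocks of 3 or 6, and 0.14 to 0.20 SD for blocks of 12. The planned adjustment would remove part of this. These figures illustrate scale and should not be set against the 0.3 in section 9.2.

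The balance check in section 6.3 (chi-square on race and site) cannot detect steering on prognosis. The baseline comparisons in the SAP cover more variables, but they compare arms and do not relate baseline status to how predictable each assignment was.

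**What to change.** **Record what was done.** State the block lengths, strata, release method and handling of minorities actually used, and reconcile section 6.3 with the SAP.

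**For any further dyads.**
- Release each assignment centrally, only after final eligibility is recorded. Move the medication check that confirms eligibility ahead of randomization, for example to the telephone screen.
- Use randomly varying block sizes (multiples of 3) within site by sex, held by the statistician and kept out of the protocol. This is a supporting measure. In a simulation with 30 dyads per stratum, guessing the least-used arm was right 51.8% of the time with sizes 6, 9 and 12, against 56.2% with fixed blocks of 6. Concealed release should come first.
- Replace the sequential assignment of minorities with the same random list.

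**For dyads already randomized.** Regress baseline plaque index, gingival index and functional status on each dyad's arm probability given the previous assignments in its stratum. Report post-randomization exclusions by arm. With about 60 dyads the regression will have limited power, so a null result would not rule out steering.

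**Cost.** A new list for any remaining dyads, arm totals that may differ by a dyad or two per stratum, and one extra analysis of existing data.

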At both sites, we will also recruit participants via alliances with clinical specialists at other medical facilities and via contacts with dementia support groups, community facilities, organizations, and at outreach events. Study related presentations and flyers will be used at the above noted venues.

Screening forms for potential subjects who are deemed ineligible or who refuse to participate will be discarded. Study team will have a database of the ineligible subjects to ensure that the study does not unnecessarily contact an individual multiple times. This database will only include the name and phone number of the potential subject and no additional PHI.

We have extensive experience in recruiting and retaining older adults, including historically under-represented populations, in longitudinal studies. In regard to under-represented groups, particularly minorities, for several years, the Duke Bryan Alzheimer's Disease Research Center (Duke ADRC) has focused efforts on developing relationships with minorities in the community through targeted outreach events. These efforts have resulted in our meeting goals of between 15 – 50% enrollment of African Americans for various studies. We will leverage these already established relationships to recruit for the present study.

We expect these recruitment sources will meet our enrollment goals because of large volume of patients at these sites. In addition, often those patients who seek treatment at academic sites have an interest in participating in clinical trials. More importantly, we have successfully recruited a diverse group of participants from the two Duke sources for our pilot studies described above and numerous prior other studies.

Our plans to retain participants in this six-month intervention include 1) ensuring that the individuals understand the purpose and benefit of the study, 2) being responsive to their inquiries, and 3) sending visit confirmation letters and visit reminder phone calls. Our incentive fee schedule is structured to pay a larger amount at the last visit, which may have some influence on retention. We think the factor that most impacts participants' decision to complete a study is a sense that the research team respects them as individuals and is committed to improving the lives of those with mild dementia.

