*Target accrual: 120 dyads

Study Design

This is a three parallel arm randomized controlled trial (RCT) to evaluate the effectiveness of a care partner-assisted intervention to improve oral hygiene in individuals (≥ 60 years) with mild dementia. Participant-care-partner dyads were randomized into 1 of 3 groups: Treatment Group 1 (**TG1**), Treatment Group 2 (**TG2**), and the Control Group (**CG**) stratified by site. **TG1** and **TG2** were given smart electronic toothbrushes. Only **TG2** will receive in-home and telephone coaching throughout the duration of the study and were instructed to record daily brushing habits. The coaching sessions included individualized instruction on oral hygiene technique, cueing strategy development, or oral hygiene monitoring and coaching. **TG1** and **CG** did not receive coaching sessions. While randomization occurred at the dyad level (participant-care partner), primary study outcomes will be assessed at the participant level. The study duration was 6 months, including a 3 month intervention phase, in which coaching and educational modules were delivered, followed by a 3 month maintenance phase in which no coaching or educational modules were presented to participants. Data was collected by the study team at three visits: baseline, 3-months (end of active intervention phase), and 6-months (end of three-month maintenance phase). The primary endpoint is oral hygiene (plaque index, gingival index) at 3 months, with a secondary endpoint of 6 months to explore maintenance of intervention effects.

Study Aims

Aim 1: Evaluate the effectiveness of a care partner-assisted intervention to improve oral hygiene and oral hygiene behaviors in individuals with mild dementia.

Hypothesis 1a: Compared to CG, both T1 and T2 will result in improved oral hygiene as measured by reduced plaque index, and reduced gingival index, at 3 months.

Hypothesis 1b: T2 will have higher improvement than T1, relative to CG, in oral hygiene as measured by a greater reduction in plaque index, and gingival index, at 3 months.

Aim 2: Assess changes in mediating factors/process outcomes, including communication between the dyads, oral health knowledge, and self-efficacy for both participants and care partners to understand mechanisms of the intervention.

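### Section 6.3 gives two incompatible allocation rules: a random list blocked by sex and site, and a sequential rule for minority participants that reads as a foreseeable rotation

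*Combined protocol and SAP*

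**What the plan says.** Protocol section 6.3 first sets out a conventional scheme: "Blinded randomization assignments will be determined by the statistician at the beginning of the study using a block (by sex) random allocation algorithm generated" in advance, with equal allocation to arms within site. On the blocks it says: "Each randomization block will be composed of two units male and female in each treatment arm by site". Shortly afterwards, in the same paragraph as the block description, comes the separate rule: "As minorities are recruited, they will sequentially be assigned to each group". The section does not say whether this sequence is random, how it fits the sex and site blocks, who holds it, or how the next assignment is concealed.

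The same section explains that visit procedures differ by arm; "thus, the research staff is not blind to the participant's assigned group". On timing, "randomization must be done prior to the first visit".

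Section 8.1 (Screening) says: "Preliminary eligibility will be determined by the study coordinator at the end of the call". The PI or designee at the site then makes the final eligibility decision. Section 6.2.1 has coordinators and PIs debriefing weekly.

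The SAP (Study Design) says: "Participant-care-partner dyads were randomized into 1 of 3 groups", with site as the only stratification factor. It has no rule for race.

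**The concern.** A list drawn in advance and a rule that operates as minority participants are recruited cannot both govern the same dyad. If minority dyads were taken through the arms in turn, their allocation was deterministic and anyone who knew the earlier assignments could work out the next one. This is an open-label trial. The people who decide eligibility are not said to be kept from past assignments, and two of the eight exclusion criteria in section 5.2 are left to the investigator's opinion. Foreknowledge of the arm could then influence which minority dyads are admitted. For those dyads the comparison would lose the protection of randomization, and the SAP's tests and intervals would lack their usual justification.

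The planned analysis would not reveal or absorb this. The model in the SAP (Aim 1) names site, baseline index scores and baseline functional status as covariates, but not race. The stated fallback steps, last observation carried forward and alternative distributions, do not concern allocation.

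**Working it through.** The plan gives no figure on this point, so there is none to reproduce. The check has two parts.

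**1. The text.** Two readings would make the sequential sentence harmless.
- It could mean taking the next entry on the random list. Every dyad would be allocated that way, so a sentence about minority participants alone would be redundant.
- It could mean a separate randomized stratum for race. The block description names only sex and site, and the SAP names only site.

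Neither reading is stated. Rotation is the plain one.

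**2. How foreseeable the arm would be.** The measure is the expected share of correct guesses by someone who sees all earlier assignments in the stratum and always picks the likeliest arm.

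*Simple randomization to three arms:* 1/3 = 33.3%.

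*Random permuted blocks, block size known.* Section 6.3 leaves the size open, so several are shown.
- 3 slots, one per arm: (1/3 + 1/2 + 1)/3 = 61.1%.
- 6 slots, two per arm. Let g(a,b,c) be the expected number of correct guesses with a, b and c slots left.
  - g(1,1,1) = 1/3 + 1/2 + 1 = 1.833
  - g(2,1,0) = 2/3 + (2/3)(1.5) + (1/3)(2) = 2.333
  - g(2,1,1) = 1/2 + (1/2)(1.833) + (1/2)(2.333) = 2.583
  - g(2,2,0) = 1/2 + 2.333 = 2.833
  - g(2,2,1) = 2/5 + (4/5)(2.583) + (1/5)(2.833) = 3.033
  - g(2,2,2) = 1/3 + 3.033 = 3.367, and 3.367/6 = 56.1%.
- 12 slots, four per arm, by the same recursion: 51.2%.

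*Rotation.* Assume one rotation per site, two sites, at least two minority dyads at each, and an order unknown at the start. At each site the first arm is guessed with probability 1/3, the second with 1/2, and every later one with certainty. With m minority dyads in total:

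rate = [m − 4 + 2(1/3 + 1/2)]/m, and m − 4 dyads have a fully determined arm.

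*Choice of m.* The SAP table shows 60 consented dyads. No minority count or target is given for this trial. Section 5.5 says of earlier outreach at Duke: "These efforts have resulted in our meeting goals of between 15 – 50% enrollment of African Americans for various studies". It also gives about 79% White at one NYU clinic, so about 21% other. Applying these shares to 60 is an assumption.

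| Assumed share | m | Fully determined | Correct-guess rate |
|---|---|---|---|
| 15% | 9 | 5 (8.3% of 60) | (5 + 1.667)/9 = 74.1% |
| 21% | 12.6 | 8.6 (14.3%) | (8.6 + 1.667)/12.6 = 81.5% |
| 50% | 30 | 26 (43.3%) | (26 + 1.667)/30 = 92.2% |

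Across the assumed range a rotation is more predictable than any block size the protocol's wording allows.

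**The case against.** The best defence is that rotation is inferred. The section calls the algorithm random and the trial randomized. The next sentence plans chi-square tests of race by group to check randomization balance, which would have little purpose if minority dyads had been rotated evenly. The SAP, written in the past tense, says dyads were randomized and mentions no race rule.

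This stands as far as conduct goes: the documents do not show that a rotation was run. It does not rescue the text. A balance check by race sits equally well beside a rule meant to force that balance, and the SAP's general statement does not say what happened to the minority rule. If another rule was used, section 6.3 still fails to describe it.

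A reader might infer several stronger things that the documents do not support.
- *That the staff who decide eligibility also assign the arm.* Section 6.3 gives assignment to the statistician. The supported point is that eligibility staff could foresee it.
- *That 9 to 30 dyads were in fact allocated non-randomly.* The shares come from other studies, and the rule in use is unknown.
- *That the next arm was known with certainty.* With an unknown starting order, the first two minority dyads at each site are not determined.
- *That equal allocation was broken.* The consented totals are 20, 20 and 20. Any imbalance would have to lie within sex or site, which is not reported.
- *That the person giving final eligibility personally saw earlier visits.* Visit attendance and recording checks fall to a PI or designee, possibly a different person. The route that is stated is unblinded research staff plus weekly debriefing.

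**Conclusion.** The contradiction in section 6.3 is real, and nothing else in the protocol or SAP repairs it. Followed as written, the sequential rule would replace random allocation for minority dyads with a largely foreseeable one: about 74% to 92% correct guesses, against 56% under blocks of 6 (51% to 61% over the possible block sizes). These figures rest on one rotation per site, an order unknown at the start, full sight of earlier assignments, and minority shares of 15% to 50% borrowed from elsewhere. Non-random allocation in practice, and any resulting bias, are not established. The question is whether part of the primary comparison is randomized at all, so it should be settled before the analysis.

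**What to change.** **Protocol 6.3, for any further enrolment.** Delete the sequential sentence and allocate every dyad from the concealed random list. If racial balance is wanted, make minority status a stratum with random assignment inside it. In either case, release the arm only after final eligibility has been recorded.

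**SAP, for dyads already enrolled.** State which rule was actually used for minority dyads, whether the sequence was random, who held it and how it was concealed. If it was random, that statement is enough. If it was a rotation:
- report how many dyads were allocated that way in each arm;
- do not describe those dyads as randomized;
- add a sensitivity analysis of the 3-month plaque and gingival contrasts restricted to dyads allocated from the random list.

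**Cost.** One sentence in the protocol, one statement in the SAP and, if needed, one count and one analysis. Dropping the rule gives slightly less exact racial balance. The restricted analysis would exclude minority dyads and could be imprecise: at the upper assumed share, (60 − 30)/3 = 10 dyads per arm before dropout; at the lower, (60 − 9)/3 = 17. It can only be supportive.
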